# 6.3.6 Withdrawal criteria and procedures

The subject **MUST** be withdrawn from the investigation for any of the following reasons:

1. Withdrawal of consent: At any time during the investigation and without giving reasons, a subject may decline to participate further. The subject will not suffer any disadvantage as a result.

The subject **MAY** be withdrawn from the investigation for any of the following reasons:

- 1. Occurrence of an AE which requires a premature termination of the treatment or precludes followup of the subject (e.g., COVID-19)
- 2. A major CIP deviation, which may interfere with evaluation of the treatment outcome (e.g., additional aesthetic correction of the defect during the course of the investigation, use of prohibited medication, or similar)
- 3. Investigator's decision, triggered by safety, behavioural or administrative reasons
- 4. Pregnancy; **Note:** pregnant women **must** be withdrawn from **further treatment**; However, pregnant women may remain in the study for safety assessments during the scheduled study visits.
- 5. Subjects with abnormal clinically significant changes in visual examination after treatment **must** be withdrawn from **further treatment** in case an eye specialist confirms that the result is related to a vascular injection of the dermal filler (see section 6.4.8 and section 16.1).

The subjects may remain in the study at least for safety assessments during the scheduled study visits.

6. Subjects who experience neurological symptoms indicative of a vaso-occlusional event after treatment **must** be withdrawn from **further treatment** in case a neurologist confirms that the result is related to a vascular injection of the dermal filler (see section 6.4.9, also see section 16.1).

The subjects may remain in the study at least for safety assessments during the scheduled study visits.

Reasons, circumstances and findings related to early withdrawal should be fully described in the subject's source records and the eCRF respecting the subject's rights.

Attempts should be made to perform an early termination visit, which should consist of the assessments planned for Visit 9 (SV1), Visit SV2 to SV4 or Visit RT5 (depending on the study phase) – also see section 6.5.16. In the event that the withdrawal is caused by an AE, the procedures stated in section 14 must be followed.

Efforts should be made, however, to get in touch with subjects who did not attend a scheduled visit and clarify the reason for default. The two attempts with also sending a registered letter to subject must be made and documented to try and make contact. If the subject is unreachable, a corresponding note should be provided in the subject's source record.

Depending on the time point of withdrawal, a withdrawn subject is referred to as either "screening failure" or "withdrawal" (see section 6.3.11).

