# 4.3 **Possible interactions with concomitant medical treatments**

No studies on drug interactions with saypha® VOLUME Lidocaine have been conducted in humans.

- Both devices must not be used in subjects on immunosuppressive therapy (also see Exclusion Criterion (ExC) #8; section 6.3.3; ExC#9 in section 6.3.5).
- Use of anticoagulant, antiplatelet, nonsteroidal anti-inflammatory drugs or thrombolytic drugs may increase the risk of bleeding or bruising (such as acetylsalicylic acid, clopidogrel, ticagrelor, and warfarin, heparin, enoxaparin, or apixaban). The subject should be asked about use of such medications (also see ExC #15; section 6.3.3, ExC#16 in section 6.3.5).
- Sodium hyaluronate is incompatible with quaternary ammonium compounds such as benzalkonium chloride solutions, hence the device should never be placed in contact with these substances or with medical-surgical instruments that have been in contact with these substances.

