## 6.3.9 Prohibited treatments

The following medications and treatments are **prohibited prior to start** of the investigation (Visit 1) and **during the entire investigation**, if not stated otherwise below (also refer to the respective ExC in section 6.3.3 to 6.3.5):

- History or presence of any autoimmune or connective tissue disease, or current treatment with immune therapy
- Previous facial plastic surgery, tissue augmentation with silicone, fat or another non-absorbable substance (permanent fillers) in the area of device application and during the entire investigation
- Implantation of dermal fillers in the treatment area within the preceding 24 months prior to Visit 1 (Screening) and during the entire investigation
- Subject has received any of the following aesthetic treatments in the midface area, e.g.
  - laser therapy, absorbable and non-absorbable sutures (threads), dermabrasion, mesotherapy, micro-needling and/or botulinum toxin (including treatment of crow's feet in the outer eye region) within the last 12 months prior to Visit 1 and during the entire investigation
  - o chemical peeling within the last three months prior to Visit 1 and during the entire

investigation,

or is planning to undergo such procedures during the investigation

- Facial lipolysis, including submental fat treatments, within the previous 12 months prior to Visit 1 (Screening) and during the entire investigation
- Bariatric surgery within 12 months prior to Visit 1 (Screening) and during the entire investigation
- Anticoagulant, antiplatelet, or thrombolytic drugs, or anti-inflammatory drugs (oral/injectable corticosteroids or non-steroidal anti-inflammatory drugs, e.g., Motrin® or Advil®) or other substances known to increase coagulation time (vitamins or herbal supplements, e.g., St. John's Wort, high doses of vitamin E supplements) from ten days pre- until seven days after each injection of the device
- Planned dental/oral surgery or modification (bridge-work, implants) within four weeks prior to baseline and repeat-treatment device injection and to a minimum of four weeks post device injections
- Current or previous treatment with another investigational drug and/or medical device or participation in another clinical study (within 30 days of Visit 1 (Screening) and entire investigation)
- Change in eating habits that result in a weight gain or loss >10% during the entire investigation

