#### Per-Protocol Set (PPS):

The PPS is defined as a subset of the subjects in the FAS without major protocol deviation(s) affecting the primary effectiveness endpoint and assessed as 'major excluding from PPS'.

The relevance of protocol deviations will be assessed at the interim and final Data Review Meetings (DRMs). Protocol deviations will be assessed as either "minor" or "major". Major protocol deviations that could directly interfere with analysis of the primary effectiveness endpoint will be further assessed as either 'major *excluding* from PPS' or `major *not* excluding from PPS'. Randomization errors will be considered 'major excluding from PPS'.

The criteria for this assessment will be defined before analysis in Protocol Deviation Manual. Listings will be prepared to assess the eligibility of all subjects during the (i)DRM.

All effectiveness analyses for the initial treatment phase will be conducted using the PPS and the FAS. The effectiveness analysis for the repeat treatment phase will be conducted using the FAS only. Safety analyses will be based on the SAF.

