# 10 Deviations from the clinical investigation plan

A CIP deviation is a failure to follow, intentionally or unintentionally, the requirements of the CIP. As required by national regulation or guidelines, requests for deviations and reports of deviations will be provided to the IRB/EC if the deviation affects subject's rights, safety and well-being, or the scientific integrity of the clinical investigation.

Under emergency circumstances, deviations from the CIP may proceed without prior approval by the sponsor and favourable opinion of the IRB/EC if the rights, safety and well-being of human subjects need to be protected. Such deviations will - however - be documented and reported to the sponsor and the IRB/EC as soon as possible in accordance with national regulations. **No waivers to the CIP will be granted by the sponsor.** 

The investigator must maintain accurate, complete and current records of any deviation from the CIP, including the date and reason for each deviation.

The investigator shall notify the sponsor and the reviewing IRB (as applicable) of any deviation from the CIP made to protect the life or physical well-being of a subject in emergency as soon as possible, but in no event later than five working days after the emergency occurred.

All CIP deviations will be listed and their impact on evaluability of respective subjects will be discussed during the interim DRM and during DRM prior to the hard data base lock.

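### Protocol 6.3.6 allows follow-up to end before Week 24 for a major deviation or an unblinded investigator's behavioural or administrative decision, creating avoidable FAS non-responders at a modest cost in power

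*Protocol*

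**What the plan says.** Section 6.3.6 of the protocol lists reasons for which a subject may be withdrawn from the investigation. Item 2 is "A major CIP deviation, which may interfere with evaluation of the treatment outcome", with examples that include "use of prohibited medication, or similar". Item 3 is the investigator's decision, "triggered by safety, behavioural or administrative reasons".

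Items 4 to 6 (pregnancy, visual findings, neurological findings) are built differently. They require withdrawal from further treatment only. For the visual and neurological cases the text adds: "The subjects may remain in the study at least for safety assessments during the scheduled study visits". Items 2 and 3 make no such separation.

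Other sections set the consequences:

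- 6.1.3: the treating investigator knows the allocation.
- 6.3.7: withdrawn subjects are not replaced.
- 6.3.6 and 6.5.16: an early termination visit including the MVDSS is to be attempted. Nothing says that this score may stand in for Week 24.
- 7.3.7: a missing Week 24 score is a non-response in the primary FAS analysis, and non-inferiority needs consistent results in PPS and FAS.
- 7.1: very few missing-data non-responders are expected.
- 7.2 and 10: deviations are graded at the Data Review Meetings, including a class of major deviations that do not exclude from the PPS. Section 10 states: "All CIP deviations will be listed and their impact on evaluability of respective subjects will be discussed during the interim DRM".

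**The concern.** The protocol already has a process for deviations: record them, keep the data, and decide at the Data Review Meeting whether the subject stays in the PPS. Withdrawal under item 2 bypasses it. Once follow-up has ended there is no Week 24 score to evaluate, whatever the meeting decides. Item 3 has the same effect for reasons that need have nothing to do with the outcome, on the judgement of someone who knows the device.

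The FAS is described in 7.2 as following the intention-to-treat principle, which calls for continued observation of subjects who deviate. Under the non-responder rule, each early withdrawal lowers the observed FAS response rate. At stake is power that could have been kept, and a FAS result that depends in part on unblinded discretion.

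**Working it through.** **Inputs.** Farrington-Manning test, margin −0.10, one-sided 0.025 (7.1, 7.3.7). Test response 0.856 (7.1). The comparator rate is not legible and is assumed to be 0.856. Evaluable 437, of whom 291 test, hence 437 − 291 = 146 comparator. Randomised 486 = 324 + 162, with 10% PPS exclusion. No withdrawal rate is given, so the rates below are illustrative.

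**Reproducing the plan's power.** Under the null difference of −0.10 the restricted estimates are 0.8078 (test) and 0.9078 (comparator).

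- s0 = √(0.8078·0.1922/291 + 0.9078·0.0922/146) = 0.0333
- s1 = √(0.856·0.144·(1/291 + 1/146)) = 0.0356
- z = (0.10 − 1.96·0.0333)/0.0356 = 0.977, so power = 83.6%; exact enumeration gives 84.4%.

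This agrees with the power above 83% given in the Amendment 5 table (19.5). The unpooled formula gives z = 0.10/0.0356 − 1.96 = 0.85, power 80.2%, which matches the 80% stated there for the previous method. Equal rates are therefore a reasonable assumption.

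**FAS with loss.** If a share w of each arm has no Week 24 score, the FAS response rate becomes 0.856·(1 − w) at 324/162.

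**Both sets.** Joint passing was simulated with the PPS at 291/146 and 33/16 subjects excluded. Lost subjects fall among the excluded and are unrelated to outcome; excluded subjects who are not lost keep their observed score in the FAS. Model A lets the number lost vary more than model B.

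| Loss per arm | FAS power (exact) | Both pass, A | Both pass, B |
|---|---|---|---|
| 0% | 87.9% | 83.0% | 83.0% |
| 1% | 86.3% | 81.8% | 81.9% |
| 2% | 84.7% | 80.4% | 80.7% |
| 3% | 83.1% | 79.0% | 79.7% |

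One per cent per arm is 3.24 + 1.62, about 5 subjects. The step per 1% is 1.2, 1.4 and 1.4 points in A, and 1.1, 1.2 and 1.0 in B: 1.0 to 1.4 points overall. Half a per cent (2 to 3 subjects) costs about 0.6 points (83.0% to 82.4%).

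**Sensitivity to the comparator rate (model A).** At 84.6%, joint power is 88.5% with no loss and 86.6% at 2%, or (88.5 − 86.6)/2 ≈ 1.0 point per 1%. At 86.6% it is 75.7% and 72.6%, or (75.7 − 72.6)/2 ≈ 1.6 points per 1%.

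**False claims.** With the truth at the margin (75.6% v 85.6%), both sets pass in 1.9% of trials with no loss, and in 2.7% with 3% test against 8% comparator loss or with 5% comparator-only loss. Joint passing cannot exceed PPS passing, and loss unrelated to outcome leaves the PPS comparison undisturbed.

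**The case against.** The clause is permissive, and no passage says such withdrawals will be routine. Section 6.3.6 asks for contact attempts when a visit is missed and for an early termination visit with the MVDSS. Section 7.3.7 plans a complete-case analysis and multiple imputation under MNAR, both of which bear on how far the FAS result depends on who was lost. Section 7.1's expectation that the larger FAS holds power is sound: FAS power is still 83.1% at 3% loss. All of this stands and limits the size of the point. It does not answer why the score should be given up at all.

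Four stronger readings might be inferred and are not supported:

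- **That the clause drives joint power below 80%.** In model A that happens at about 2.3% loss per arm, but this is loss from any cause. Consent withdrawal and loss to follow-up count towards it and the fix does not touch them. The 83% starting figure comes from the both-sets rule, not from 6.3.6.
- **That it inflates false non-inferiority.** For the FAS alone, 5% comparator-only loss would give 20.9% at the margin. The decision also needs the PPS, and joint passing stays at 2.7%. Outcome-related selective withdrawal could escape this guard, but nothing in the protocol indicates it, or that loss would fall in one arm.
- **That a subject could be withdrawn merely for a drug that causes bruising.** Section 6.3.9 prohibits "Anticoagulant, antiplatelet, or thrombolytic drugs, or anti-inflammatory drugs" around injections, and 4.3 states the worry as bleeding or bruising. But item 2 covers only deviations that may interfere with outcome evaluation, so such use would not by itself qualify.
- **That the Data Review Meeting would have kept most of these subjects in the PPS.** The cost would then be 1.5 to 1.7 points per 1%. Item 2's wording is close to the 7.2 description of deviations that could lead to exclusion, so this is the less likely case. Nor is the meeting blind: 6.1.3 lists sponsor and CRO staff, including the biostatistician, as unblinded.

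**Conclusion.** The point holds as a small design weakness. Items 2 and 3 of 6.3.6 permit avoidable loss of the primary score, where items 4 to 6 show that the protocol can separate stopping treatment from ending follow-up. The price is roughly 1.0 to 1.4 points of joint PPS-and-FAS power, from about 83%, for each 1% of subjects per arm withdrawn under the clause. This assumes a comparator rate of 85.6%, loss unrelated to outcome, and lost subjects inside the planned 10% PPS exclusion. How many would be withdrawn this way is unknown. On the same assumptions, false non-inferiority stays at or below about 2.7%.

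The remaining benefit is uncertain. The Amendment 5 table (19.5) indicates that recruitment was complete by version 6.0, and the protocol does not say how many subjects have yet to reach Week 24. The change is worth considering; the trial's conclusion does not hang on it.

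**What to change.** In 6.3.6, state that a protocol deviation, or a behavioural or administrative reason, is not in itself a ground for ending follow-up before Week 24. Such subjects continue the scheduled visits, including the blinded Week 24 MVDSS, unless consent is withdrawn or follow-up is impossible (for example, site closure). The deviation is then handled through the PPS decision at the Data Review Meeting. This concerns data collection only, not treatment.

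The cost is a wording change, a reminder to sites, and a few more attendances at visits already scheduled. Only subjects who have not yet reached Week 24 can benefit.

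A separate matter to correct in the same edit: 6.4.4 says a subject who becomes pregnant must be withdrawn from the study, while 6.3.6 and 14.5.5 let her remain for safety assessments. These passages contradict each other and must be reconciled.

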## 6.3.7 Replacement of subjects

Subjects withdrawn from the investigation or lost for follow-up will not be replaced.

No re-screening is allowed. An exception may be granted with prior approval of the sponsor in case that subjects are withdrawn due to restrictions that might occur in the context of the ongoing COVID-19 pandemic (e.g., in case conduction of the clinical investigation in a protocol-conformal manner is no longer possible due to a new pandemic situation comparable to the COVID-19 pandemic in spring 2020).

## 6.3.8 Life-style and other restrictions

#### **Contraception**

**Women of childbearing potential** participating should not be pregnant and should use effective contraception methods throughout the clinical investigation or avoid unprotected sexual intercourse. Any pregnancy occurring in study subjects should be reported and followed-up as described in section 14.

**Note 1:** A woman is considered to be of childbearing potential (WOCBP) if fertile, following menarche and until becoming postmenopausal unless permanently sterile. Permanent sterilization methods include hysterectomy, bilateral salpingectomy and bilateral oophorectomy. A postmenopausal state is defined as no menses for 12 months without an alternative medical cause.

**Note 2:** Effective methods of birth control include: combined (estrogen and progestogen containing) hormonal contraception associated with inhibition of ovulation (oral, intravaginal, transdermal), progestogen-only hormonal contraception associated with inhibition of ovulation (oral, injectable, implantable), intrauterine device (IUD), intrauterine hormone-releasing system (IUS), bilateral tubal occlusion, vasectomized partner (provided that is the sole sexual partner of the subject and that the vasectomized partner has received medical assessment of the surgical success and sexual abstinence (if in line with the preferred and usual lifestyle of the subject and defined as refraining from heterosexual intercourse during the entire period of the trial).

**Male subjects** should use an effective contraceptive method as a reproductive damage on the seminal fluid cannot be ruled out. Male fertile participants need to ensure safe contraception to prevent their female partner of childbearing potential from becoming pregnant. Contraceptive methods include surgical sterilization or a physical barrier such as a condom when having penile-vaginal intercourse. This applies from throughout the clinical investigation. Males will be counseled to inform their female partner about the participation in the clinical investigation.

## Other restrictions

The following restrictions apply to all subjects:

- Make-up should not be applied for 12 hours after each device injection
- Within the first 24 hours after each device injection, subjects should avoid strenuous exercise and extensive sun or heat exposure. Exposure to any of the above may cause temporary redness, swelling, and/or itching at the treatment sites.

Note: If the treated area is swollen, an ice pack may be applied to the site for a short period.

- Prolonged exposure to sunlight or ultraviolet (UV) radiation must be avoided for one week after each device injection.
- To minimize the risk of product mobility, the subject should be advised to avoid massaging the treatment site or applying pressure to this area for one week following each device injection (exception: a light massage may be applied after injection of the device for uniform distribution of the filler by the investigator see Table 15 in section 6.2.2)
- Use of saunas or Turkish baths is prohibited for one week after each device injection.
- Beard longer than three-day beard, or excessive facial hair that could interfere in evaluation of treatment as judged by the investigator (see ExC#17 in see section 6.3.3 and ExC#18 in section 6.3.5)

## 6.3.9 Prohibited treatments

The following medications and treatments are **prohibited prior to start** of the investigation (Visit 1) and **during the entire investigation**, if not stated otherwise below (also refer to the respective ExC in section 6.3.3 to 6.3.5):

- History or presence of any autoimmune or connective tissue disease, or current treatment with immune therapy
- Previous facial plastic surgery, tissue augmentation with silicone, fat or another non-absorbable substance (permanent fillers) in the area of device application and during the entire investigation
- Implantation of dermal fillers in the treatment area within the preceding 24 months prior to Visit 1 (Screening) and during the entire investigation
- Subject has received any of the following aesthetic treatments in the midface area, e.g.
  - laser therapy, absorbable and non-absorbable sutures (threads), dermabrasion, mesotherapy, micro-needling and/or botulinum toxin (including treatment of crow's feet in the outer eye region) within the last 12 months prior to Visit 1 and during the entire investigation
  - o chemical peeling within the last three months prior to Visit 1 and during the entire

investigation,

or is planning to undergo such procedures during the investigation

- Facial lipolysis, including submental fat treatments, within the previous 12 months prior to Visit 1 (Screening) and during the entire investigation
- Bariatric surgery within 12 months prior to Visit 1 (Screening) and during the entire investigation
- Anticoagulant, antiplatelet, or thrombolytic drugs, or anti-inflammatory drugs (oral/injectable corticosteroids or non-steroidal anti-inflammatory drugs, e.g., Motrin® or Advil®) or other substances known to increase coagulation time (vitamins or herbal supplements, e.g., St. John's Wort, high doses of vitamin E supplements) from ten days pre- until seven days after each injection of the device
- Planned dental/oral surgery or modification (bridge-work, implants) within four weeks prior to baseline and repeat-treatment device injection and to a minimum of four weeks post device injections
- Current or previous treatment with another investigational drug and/or medical device or participation in another clinical study (within 30 days of Visit 1 (Screening) and entire investigation)
- Change in eating habits that result in a weight gain or loss >10% during the entire investigation
- According to IB (section 8.1.5) and IFU for [14] (section B. Health Care Professional Instructions #5) sensitive skin may be pre-treated using a local anaesthetic patch or cream or injectable anesthesia. However, **injectable** anaesthesia is **not allowed** to manage pain during and after injection in this investigation. Additional **topical** anaesthetic (patch or cream) is allowed but should be avoided possible (i.e., if the subject agrees) to not falsify the pain assessment (as collected via Numerical Pain Rating Scale; see section 6.4.14).

